### **3.2 Optional blood samples**

Optional consent may be provided for the collection of participant blood samples for use in future ethically approved research. Consent will be collected as per section 2.7 of the RELEASE domain protocol and section 4.2.3 of the CoReCCT master protocol.

20mL of blood will be taken at baseline, day 3 and day 7. Blood samples will be obtained for each trial arm. The baseline sample will be collected prior to intervention commencement (either pre- or post-randomisation). Where this is not possible, samples should not be obtained at any timepoint. Failure to collect optional blood samples is not considered non-compliant with the trial protocol.

The collected samples will be labelled with the participant's trial number and stored at -80°C at the hospital site. Samples will be transported in batches to the Queen's University Belfast, at a time of mutual convenience, and stored beyond completion of the study. This activity will be coordinated by the WCTU trial team. Any samples not used will be disposed of in accordance with local policy and applicable regulations.

### **3.3 Follow-up Procedures**

Follow-up questionnaires at 2 months and 6 months will capture health-related quality of life and healthcare resource use. Follow up time points and management of follow up questionnaires are aligned over all CoReCCT domains and managed by WCTU. Refer to section 6 of the CoReCCT Master Protocol for further details.

### 4. ADVERSE EVENT MANAGEMENT

In order to accurately assess and report SAEs relevant to RELEASE, the CoReCCT Master Protocol must be read in conjunction with section 4.1 below.

Section 7 of the CoReCCT Master Protocol describes the CoReCCT Safety Reporting Flowchart and provides details on these adverse event management topics:

- Definitions of SAEs
- Assessing and reporting SAEs
- Causality Assessment of SAEs
- Expectedness Assessment of Related SAEs
- Expedited Reporting of Related and Unexpected SAEs to REC

### 4.1 Pre Specified Complications

As per the CoReCCT Safety Reporting Flowchart, adverse events that 1) occur at sites between randomisation and hospital discharge and 2) are not present on the CoReCCT Exemption List, must be reviewed for their presence on the RELEASE Pre-Specified Complications List as given below.

Pre-Specified Complications List (that occur up to Day 10 post randomisation)

Barotrauma (including pneumothorax, pneumomediastinum, subcutaneous emphysema)

Hypotension requiring new vasopressors or increase in vasopressors of more than 0.2 microgram/kg/min

As per the CoReCCT Safety Reporting Flowchart, if the event is present on the Pre-Specified Complications List and occurred up to Day 10 post-randomisation, the event must be recorded on the appropriate CRF as an outcome and does not need to be reported on an SAE form. Pre specified complications which occur beyond Day 10 post-randomisation will not be recorded. If the event is not on the list, it must be assessed for seriousness and the remainder of the flowchart should be followed to determine next steps.

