### 2.4.2 Secondary objective

To determine the effect of APRV compared to conventional lung protective ventilation on the following:

- All-cause mortality at 2 and 6 months
- First extubation
- Reintubation
- Use of non-invasive ventilation following extubation
- CCU and hospital length of stay
- Serious adverse events up to hospital discharge
- Health related quality of life (EQ-5D-5L) at 2 and 6 months after randomisation
- Acute health care use at 2 and 6 months after randomisation
- Within-trial cost-utility analysis from an NHS hospital care perspective (see Section 6.5).

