### 2.9.4.2 Other Clinical Management

Responsibility for all other management decisions remains the responsibility of the attending physicians and CCU team.

The intervention (APRV or control) will continue until one of the following criteria is met:

- 60 days after randomisation
- Successful unassisted breathing (at 48 hours with no further requirement for inspiratory support or extracorporeal lung support. See section 2.4.3 for full definition)
- Trial intervention-related serious adverse event
- Death or discontinuation of active treatment
- Withdrawal of consent

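### Section 4.1 leaves barotrauma and vasopressor-requiring hypotension after Day 10 with no recording route in either arm, although serious adverse events to hospital discharge are a secondary outcome

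*Protocol*

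**What the plan says.** Protocol section 4.1 applies to adverse events between randomisation and hospital discharge that are not on the master protocol's exemption list. It gives a list headed "Pre-Specified Complications List (that occur up to Day 10 post randomisation" (closing bracket omitted here). The list has two entries: "Barotrauma (including pneumothorax, pneumomediastinum, subcutaneous emphysema" (likewise) and "Hypotension requiring new vasopressors or increase in vasopressors of more than 0.2 microgram/kg/min".

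Three instructions follow.

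- For a listed event up to Day 10, "the event must be recorded on the appropriate CRF as an outcome and does not need to be reported on an SAE form".
- For later listed events: "Pre specified complications which occur beyond Day 10 post-randomisation will not be recorded".
- For everything else: "If the event is not on the list, it must be assessed for seriousness".

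Elsewhere, section 2.4.2 names "Serious adverse events up to hospital discharge" as a secondary outcome. The Trial Summary does the same, and the schedule in section 3.1 marks SAEs up to hospital discharge. Section 2.9.4.2 ends the intervention at the first of several criteria, the latest by calendar being "60 days after randomisation". Section 2.9.2.5 keeps participants on APRV until extubation.

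**The concern.** The two listed events are the only complications that the protocol itself pre-specifies for this comparison. Section 4.1 switches off their recording at Day 10, while the trial still follows SAEs to discharge and may still be delivering the allocated ventilation. If sites obey the sentence, a late serious event of either type leaves no trace in the complication data or the SAE data, and events never recorded may not be recoverable at analysis. The late part of the safety comparison would then lack these two event types, in the patients ventilated longest.

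Two other sections add to the tension. Section 2.9.4.3 expects a new air leak or cardiovascular instability during APRV and sets no Day 10 limit. Section 2.9.4.2 makes an intervention-related SAE one of the criteria for ending the intervention, yet section 4.1 gives a late listed event no SAE route.

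**Working it through.** **1. The routes in section 4.1, side by side**

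| Event | Complications CRF | Seriousness assessment / SAE form |
|---|---|---|
| Listed type, up to Day 10 | Yes | SAE form not needed |
| Listed type, after Day 10 | No | No route stated |
| Type not on the list, to hospital discharge | No | Yes |

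The middle row is empty. The sentence governing the first row treats being on the list and occurring by Day 10 as two separate conditions. A late pneumothorax meets the first and fails the second. The third row is reached only by failing the first. The late event therefore falls between the two, and the sentence on late events then says that it is not recorded.

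**2. What that row conflicts with**

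- The secondary outcome (Trial Summary, section 2.4.2) and the schedule (section 3.1) run SAEs to hospital discharge without exempting any event type.
- Section 4.1 opens with the window from randomisation to hospital discharge.
- The list heading builds the Day 10 limit into the list, which could mean that late events are off the list and go to seriousness assessment. The explicit sentence says the opposite.

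**3. Size of the window: inputs**

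From section 6.1: control median about 9 days, a reduction of 2 days (hence 7 days on APRV), 355 per arm, 90% power, 5% significance (taken as two-sided), 5% loss. The exponential shape is an assumption, because the protocol gives no distribution.

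*Do these inputs reproduce the plan's own figure?* With exponential times the hazard ratio is 7/9 in size. Freedman events = (1.960 + 1.282)² × [(1 + 7/9)/(1 − 7/9)]² = 10.507 × 64 = 673 after rounding up. Per arm: 673/2 rounds up to 337, and 337/0.95 rounds up to 355, so the total is 710, as stated. Schoenfeld's formula gives 666 events and 702 patients, which is close. The medians and shape are therefore consistent with the planned sample size.

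**4. Size of the window: result**

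P(still in the ventilation episode at Day 10) = 2^(−10/median).

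| Median (days) | Share past Day 10 | Of 355 |
|---|---|---|
| 9 (control, planning) | 2^(−10/9) = 0.463 | about 164 |
| 7 (APRV, planning) | 2^(−10/7) = 0.371 | about 132 |
| 6 (shortest cited in section 6.1) | 2^(−10/6) = 0.315 | about 112 |
| 14.1 (longest cited in section 6.1) | 2^(−10/14.1) = 0.612 | about 217 |

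The planning rows total about 296 of 710. If time is capped at day 60, the share of ventilation time falling after Day 10 is 0.458 with a 9-day median and 0.370 with a 7-day median.

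**The case against.** Several points on the other side are fair.

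- **The master protocol.** Section 4 requires the CoReCCT Master Protocol to be read together with section 4.1. Its section 7, which holds the SAE definitions and the reporting flowchart, is not among the documents. It might supply another route. This stands as a limit on certainty. It does not remove the conflict, because section 4.1 gives sites an explicit trial-specific instruction.
- **The list heading.** If the Day 10 limit belongs to the list, a Day 12 event is unlisted and is assessed for seriousness. The sentence on late events could then mean only that they are not entered on the complications form. That may be what was intended, but it is not what the sentence says, and the same edit is needed either way.
- **Day 10 is a coherent data window.** Section 3.1 collects ventilator settings, sedation, organ failure and rescue therapies up to Day 10, and section 3 restricts data collection to what is required. A fixed window also gives both arms the same calendar period. This stands: a Day 10 complication rate is a legitimate choice, and extending the complications form would be a preference, not a correction.
- **The shares are not event counts.** No event rate is given, and the risk need not be constant. Section 2.9.2.2 ties hypotension on APRV to the transition and calls it transient, which points to early events for that item. The duration in section 2.4.3 also includes non-invasive and extracorporeal support, so being in the episode is not the same as being on APRV. This stands in full.

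A reader might go further and infer that the rule hides the harms of APRV in particular, that about 296 patients have unrecorded events, that all treatment lasts 60 days, or that the Data Monitoring Committee's data are shown to be undercounted. The documents support none of these. The rule applies to both arms, so the direction of any bias is unknown. The 296 are patients past Day 10, not events. Sixty days is a maximum. What the committee receives is left to the master protocol.

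**Conclusion.** The concern holds as an internal contradiction in section 4.1 that affects which safety data are collected. On its face the text gives serious barotrauma or vasopressor-requiring hypotension after Day 10 no recording route in either arm, against an SAE outcome defined to hospital discharge.

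Under the planning medians and an exponential shape, about 46% of control and 37% of APRV patients would still be in the ventilation episode when recording stops, and 31% to 61% over the durations cited in section 6.1. The number of events lost cannot be estimated from the protocol.

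The loss has limits. Unlisted SAEs are still followed to discharge, and death, ventilation duration and length of stay are still collected. Listed events up to Day 10 need no SAE form either, but they are at least captured as outcomes. The conclusion rests on section 4.1 as it stands. If section 7 of the master protocol contains an overriding route, the remaining defect is a sentence that tells sites otherwise.

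**What to change.** Replace the sentence on late events in section 4.1 with one to this effect: listed events after Day 10 are not entered on the complications form, but are assessed for seriousness through the rest of the flowchart and, when serious, reported as SAEs up to hospital discharge. Check the wording against the flowchart in section 7 of the master protocol, and align the list heading so that both say the same thing.

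Keep the Day 10 complication rate as the fixed-window comparison between arms.

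The change costs one protocol sentence, a check against a flowchart shared with other trials, and a small number of extra SAE forms at sites. It alters neither the sample size nor the primary analysis, and it does not lengthen the complications form.

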### 4.2 Expected Events

SAEs which are considered possibly related, probably related or definitely related to the study intervention will be assessed for expectedness by the Sponsor. This expectedness assessment may be supported by items such as, but not limited to associated domain working instructions and published literature.

### 5. DATA MANAGEMENT

Full details on data management are provided in sections 6 and 10 of the CoReCCT master protocol.

### 5.1 Data collection and management

Full details are listed in section 10 of the CoReCCT Master Protocol.

### 5.2 Data Shared with Third Parties

Full details are listed in section 12 of the CoReCCT Master Protocol.

### 5.3 Archiving

Full details are listed in section 13 of the CoReCCT Master Protocol.

### 6. STATISTICAL ANALYSIS

### 6.1 **Power and sample size**

The RELEASE trial will recruit a total of 710 (355 per arm) participants (using 90% power and 5% significance level).

The parameter estimates for this trial have been derived as follows:

(a) Effect size of 2-days reduction: Given our (Figure 1) and previous meta-analyses[8-11] showed a reduction of IMV duration with APRV of 3.3-5.4 days, an effect size of 2 days is conservative and can be realistically achieved.

[figure not shown]
(b) Median duration of ventilation on the control arm: the duration of ventilation varies in the UK from 7 to 14 days in reported studies (i.e., 7 days- BREATHE trial [23]; 14.1 days -OSCAR trial[24]. National reporting from the Intensive Care National Audit & Research Centre (ICNARC) Case Mix Programme Database 2019 indicates a duration of 6 days. Taking our trial population and comparing this to that reported in previous studies, we anticipate that the duration of ventilation in the control arm would be approximately 9 days.

(c) Loss to follow-up: In the previous CCU studies, loss to follow-up ranges from 0% to 3% (1.1% -BREATHE trial [23]; 0% - OSCAR trial[24] 0.4% - HARP-2 trial[25]; 0.5% - HARP trial; 3% - REST trial[26]). We have assumed a worst-case scenario here and used 5% as our loss to follow-up rate.

### 6.2 Statistical analysis of efficacy and harms

### 6.2.1 Planned recruitment rate

We will conduct an 8-month internal pilot opening 20 sites over 5 months (4 sites/month). We estimate a conservative 0.7 patients/ICU/month recruitment rate based on previous clinical trials (0.6 patients/ICU/month in first 5 months of recruitment. A realistic staggered set-up of the remaining 20 sites will follow. Total recruitment duration including the internal pilot is 32 months.

### 6.2.2 Statistical analysis plan

A full and detailed Statistical Analysis Plan (SAP) will be agreed with the Data Monitoring Committee (DMC) prior to any analysis taking place. Data will be analysed and reported according to the CONSORT statement.

### 6.2.3.1 Summary of baseline data and flow of patients

Screening log data will be collected for each site on a regular basis, and this will be scrutinised by the trial team to assess patient recruitment.

At randomisation, patient demographic data will be recorded. This will include: age, sex, body mass index.

Continuous baseline data will be summarised with descriptive statistics, including number of observation (n), mean, standard deviation, median, interquartile range and number of missing data. Categorical baseline data will be summarised with frequency counts and percentages.

### 6.2.3.2 Primary outcome analysis

Primary outcome and the Estimand Framework

In addition to the objectives, interventions and the population already stated above, the following define the Estimand framework that will be used for the RELEASE trial, in line with the ICH E9 (R1) addendum on Estimand and sensitivity analyses in clinical trials.[23]

Variable (outcome): Our main variable (outcome) of interest is ventilation duration, from the time of randomisation to successful extubation or death. 'Successful extubation' will be defined using the core outcome set[21] definition i.e., the time point a patient is free of ventilatory (invasive or non-invasive) support for >48 hours.

Summary measure and the primary Estimand: Ventilation duration will be determined as the time of successful extubation/death minus the time from the point of randomisation (in hours/mins). The statistical analysis for this outcome will be performed using the treatment policy strategy (i.e., intention-to -treat). Statistical summaries of ventilation duration will be made using median and interquartile range (IQR). We will use a Cox proportional hazard regression model to estimate the treatment difference reporting hazards ratios and their 95% confidence intervals (CIs), using both unadjusted and adjusted estimates. We will report the mean difference with 95% CIs using linear regression.

Intercurrent events (ICEs) and strategies for handling ICEs: post-randomisation events that may affect the interpretation of the primary outcome include: (a) crossover; (ii) non-adherence (including discontinuation of treatment); and (iii) death. Rates of crossover and non-adherence will be added using the principal stratum strategy. We will use the inverse probability weighted analysis method[24] to assess the treatment effect, having taken account of these events. The composite strategy will be used to assess the effect of death, with ventilation duration. We will use the Pocock's win-ratio method[25] and also assess the interaction of ventilation duration with mortality status, bearing in mind the interaction term may not be powered to detect differences.

### 6.2.3.3 Secondary outcome analysis

In general, continuous baseline and outcome data will be summarised with descriptive statistics, including n, mean, standard deviation, median, IQR and n of missing data. We will use mixed-effects linear regression models to estimate mean treatment differences (95% CI). Categorical baseline and outcome data will be summarised with frequency counts and percentages. We will use mixed-effects logistic regression models to estimate the difference in binary outcomes between treatment groups, with odds ratios and 95% CIs reported. Survival based outcomes will be analyzed using the Cox proportional hazards model with data displayed using the Kaplan-Meier plots.

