Intervention	Airway Pressure Release Ventilation (APRV). APRV is a method								
	of IMV which uses longer inspiration times followed by a brief								
	expiration. The longer inspiration time enables alveolar								
	recruitment and oxygenation while the short expiration time								
	maintains lung volume. This reduces shear-stress damage to the								
	alveoli, whilst maintaining adequate ventilation.								
Control	Standard lung protective IMV								
Follow-up Duration	6 months								
	Objectives								
Primary Outcome	Duration of invasive mechanical ventilation (time from								
	randomisation to first successful unassisted breathing or death)								
Secondary Outcomes	1. All-cause mortality at 2 and 6 months								
	2. Time to first extubation								
	3. Reintubation								
	4. Use of non-invasive ventilation following extubation								
	5. CCU and hospital length of stay								
	6. Serious adverse events up to hospital discharge								
	7. Health related quality of life (EQ-5D-5L) at 2 and 6								
	months after randomisation								
	8. Acute health care use at 2 and 6 months after								
	randomisation								
	We will conduct a within-trial cost-utility analysis from an NHS								
	hospital care perspective								
Statistical methods	Intention to treat and per protocol analyses.								
	Cox proportional hazard regression model to estimate the treatment								
	difference reporting hazards ratios and their 95% confidence intervals								
	(CIs), using both unadjusted and adjusted estimates.								
	Mean difference with 95% CIs using linear regression.								

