### 1. BACKGROUND

### 1.1 Epidemiology and burden of the condition

Approximately 130,000 adults are admitted to critical care units (CCUs) in the UK each year, 40-45% of whom require invasive mechanical ventilation (IMV).[1] Acute hypoxaemic respiratory failure (AHRF) is the most common reason for IMV and is associated with serious morbidity and a mortality which remains high at ~40%.[2] Although lifesaving, IMV can cause additional lung injury (termed ventilator induced lung injury - VILI).[3]

To minimise ventilator induced lung injury, UK guidelines recommend using IMV with a low tidal volume and low inflation pressure, generally with a short time for inspiration (breathing in) and longer time for expiration (breathing out).[4] However, injured lungs inflate slowly and deflate quickly. Consequently, most injured lungs need more time (i.e., longer inspiration) so that they can achieve a more gradual and complete inflation. A shorter expiration prevents lung collapse and injury. Therefore, the currently recommended method of IMV may perpetuate VILI leading to more days on a ventilator and increased risk of death.

Airway Pressure Release Ventilation (APRV) is an innovative ventilatory strategy available on all CCU ventilators at no additional cost to the National Health Service (NHS). APRV may improve gas exchange and minimise VILI by reducing excessive lung stretch and preventing lung collapse. [5, 6]

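### Kaplan-Meier is the stated display for time to first extubation although death before extubation competes with it; if deaths are censored, the curve overstates the share extubated

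*Protocol*

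**What the plan says.** The Trial Summary lists "Time to first extubation" among the secondary outcomes. Section 2.4.2 shortens the same item to "First extubation". Neither wording includes death as an endpoint.

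The only method given for time-to-event secondary outcomes is in section 6.2.3.3: "Survival based outcomes will be analyzed using the Cox proportional hazards model with data displayed using the Kaplan-Meier plots". The section does not say what happens to a patient who dies before extubation, and it mentions neither cumulative incidence nor competing risks.

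Death is dealt with explicitly for the primary outcome. Ventilation duration ends at successful unassisted breathing or death, and section 6.2.3.2 states: "The composite strategy will be used to assess the effect of death, with ventilation duration". That section adds a win ratio and an interaction with mortality status. All of this concerns ventilation duration, and none of it is carried over to first extubation.

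**The concern.** Death before extubation is a competing event. There are two usual ways to apply section 6.2.3.3 to this outcome, and neither gives a curve that reads as the proportion extubated.

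- **Deaths censored.** Kaplan-Meier treats those who died as still able to be extubated later, at the same rate as those still ventilated. One minus Kaplan-Meier then exceeds the share actually extubated.
- **Deaths counted as events.** The curve shows the end of ventilation by extubation or death, which is a different outcome.

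The second issue is what the comparison between arms can show. If APRV changed deaths on the ventilator and left the extubation rate unchanged, the Kaplan-Meier curves and the Cox hazard ratio for extubation would show no difference, although the proportion ever extubated would differ. This is not far-fetched here, since section 1.2 cites three reviews reporting a mortality benefit with APRV.

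**Working it through.** **The plan's own figure.** The protocol gives no figure for first extubation. Its sample size reproduces from medians of 9 and 7 days with exponential times. Freedman's formula with a ratio of 9/7, 90% power and two-sided 5% gives 673 events, and 673/0.95 = 709, or 355 per arm (710). This treats every retained patient as having an event, so the 9-day median belongs to the composite of liberation or death.

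**Inputs.**
- Median: section 6.1 says "we anticipate that the duration of ventilation in the control arm would be approximately 9 days". It is borrowed here for first extubation, for which no median is given.
- Range of medians: section 6.1 says "the duration of ventilation varies in the UK from 7 to 14 days in reported studies", and also cites 6 days from national audit data.
- Share *d* dying before any extubation: not in the protocol. Section 1.1 gives "a mortality which remains high at ~40" per cent, which is overall mortality with no time point and so only a rough upper guide. I take *d* = 10 to 40%.
- Constant hazards, with total hazard λ = ln 2/9 per day. At day 28, λt = 2.156 and 1 − exp(−λt) = 0.884.

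**Formulas.**
- True cumulative incidence of extubation: (1 − d)(1 − exp(−λt)).
- One minus Kaplan-Meier, deaths censored: 1 − exp(−(1 − d)λt).
- Curve with deaths counted as events: 1 − exp(−λt).

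**Day 28, 9-day median.**

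| d | True incidence | 1 − KM, deaths censored | Excess (points) | Excess if deaths are events (points) |
|---|---|---|---|---|
| 10% | 79.6% | 85.6% | 6.1 | 8.8 |
| 20% | 70.7% | 82.2% | 11.4 | 17.7 |
| 30% | 61.9% | 77.9% | 16.0 | 26.5 |
| 40% | 53.1% | 72.6% | 19.5 | 35.4 |

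At day 60 with d = 30%, the figures are 96.1% (deaths censored) against 69.3% (true).

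**Sensitivity, deaths censored, day 28.**
- Medians of 6 to 14 days: 7.0 to 28.0 points for d = 20 to 40%, and 3.8 to 8.1 points for d = 10%.
- Weibull shapes 0.8 to 1.3 at a 9-day median: 9.1 to 26.7 points for d = 20 to 40%.
- Deaths kept in the risk set to the end of follow-up: no gap.

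**Effect acting through deaths.** Keep the extubation hazard at (1 − d)λ in both arms and multiply the death hazard dλ by f in the APRV arm. The extubation hazard ratio is 1.00 and the censored-death curves coincide. True incidence in the APRV arm is [(1 − d)/(1 − d + fd)] × [1 − exp(−(1 − d + fd)λt)].

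- f = 0.5, day 28: 76.1% against 70.7% in control (d = 20%), 69.2% against 61.9% (d = 30%), 61.6% against 53.1% (d = 40%).
- f = 1.4, d = 30%, day 60: 62% against 69% in control, while both Kaplan-Meier curves read 96%.

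**The case against.** Section 6.2.3.3 is a general paragraph that does not name first extubation and gives no censoring rule. Section 6.2.2 leaves detail to the statistical analysis plan, which is not shown and may contain the rule for deaths. That is fair as far as the rule goes, and it is why the size is stated conditionally. It does not remove the point: Kaplan-Meier is a display method the protocol has chosen for survival-based outcomes, and under either usual reading it gives the wrong extubation probability.

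Two limits on the size also stand. The share dying before extubation may be well below 40%. Overall mortality includes deaths after extubation, patients likely to die within 24 hours are excluded, and first extubation is not limited to successful extubation. The 9-day median belongs to a different outcome, and first extubation can come earlier.

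A reader might infer that the Cox comparison of the arms is itself invalid. The documents do not support that. With deaths censored, Cox validly estimates the cause-specific hazard ratio for extubation, and a ratio of 1.00 is the correct answer when the extubation rate is unchanged. Mortality at 2 and 6 months is analysed separately. What fails is reading the ratio or the curve as the effect on the proportion extubated.

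A reader might also infer that Kaplan-Meier should be dropped for everything except mortality. It remains suitable for the primary composite, where death is an event.

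**Conclusion.** The point holds as a conditional finding on one secondary outcome. The protocol names Kaplan-Meier for survival-based secondary outcomes without separating mortality, where it is suitable, from first extubation, where death competes. If deaths are censored and 10 to 40% of patients die before any extubation, the curve overstates extubation at day 28 by about 6 to 20 points.

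That range rests on constant hazards, on a median borrowed from the primary composite, and on an assumed share of deaths. It should not be read as a measured error or as a statement that up to 40% die before extubation. The sample size and the primary analysis are unaffected.

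**What to change.** Add to section 6.2.3.3:

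> Time to first extubation will be displayed as cumulative incidence (Aalen-Johansen) with death before extubation as a competing event, with the death curve alongside. Cause-specific hazard ratios for extubation and for death will be reported, with the difference in cumulative incidence at day 28 and day 60 (or a subdistribution hazard ratio).

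Keep Kaplan-Meier for mortality and for the primary composite. Using the Trial Summary's name for the outcome in section 2.4.2 as well would be a small editorial gain.

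The cost is one sentence and a little more analysis. Extubation and mortality are both outcomes already planned, so no new outcome is needed. Reported extubation proportions will be lower than Kaplan-Meier with deaths censored would show.
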